10.2 Adverse Events

All reported AEs will be coded using the Medical Dictionary for Regulatory Activities (MedDRA) with the most current version for the purposes of summarization. NCI CTCAE Version 5.0 will be used for grading AEs. AEs will be collected and recorded for each patient from the day of signing the ICF until 30 days after last trial intervention administration or until participant started alternative anticancer therapy, whichever is sooner. Prior to receiving trial intervention, only AEs considered related to trial procedures and all SAEs will be summarized by arm, dose level, and dose schedule.

A treatment-emergent adverse event (TEAE) will be defined as any event that was not present prior to the initiation of trial intervention(s) or any event that worsens in either intensity or frequency following exposure to trial intervention(s) through 30 days after cessation of trial treatment, or until the participant starts alternate anti-cancer therapy, or the participant is taking the monotherapy treatment and starts the co-therapy olaparib, whichever occurs first. The exception are RP-3467 related SAEs which were reported until the end of trial and will be included as TEAE regardless of time of onset.

All AEs reports will be summarized by treatment regimen (Arm 1 and Arm 2), dose level and schedule (if applicable) unless otherwise specified.

Overall AE summaries will be presented for the Safety Population (unless otherwise specified). The summaries will include the following categories:

- All TEAEs
- TEAEs with CTCAE Grade 3
- TEAEs with CTCAE Grade 4
- TEAEs with CTCAE Grade 5
- DLT (based on DLT evaluable population)
- RP-3467 related TEAE
 - RP-3467 related TEAE with CTCAE Grade 3
 - RP-3467 related TEAE with CTCAE Grade 4
 - RP-3467 related TEAE with CTCAE Grade 5
- Olaparib related TEAE
 - Olaparib related TEAE with CTCAE Grade 3
 - Olaparib related TEAE with CTCAE Grade 4
 - Olaparib related TEAE with CTCAE Grade 5
- Any Serious AEs
- Any treatment-emergent serious AEs (TESAE)
- RP-3467 related TESAEs
- TEAE leading to dose reduction
- TEAE leading to dose interruption
- TEAE leading to study drug withdrawal
- RP-3467 related TEAE leading to dose reduction
- RP-3467 related TEAE leading to dose interruption

- RP-3467 related TEAEs leading to study drug withdrawal
- Olaparib related TEAE leading to dose reduction
- Olaparib related TEAE leading to dose interruption
- Olaparib related TEAE leading to study drug withdrawal

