- Adverse Event of Special interest (AESI) if any occurred as defined in the protocol
- TEAE leading to Death

Any missing onset date, causality, or severity must be queried for resolution. Unresolved missing causality will be considered “Related”.

Any missing or partial dates will be handled according to the rules outlined in section 5.4.

TEAEs will be summarized by SOC, PT unless stated otherwise. TESAEs, Related TEAEs, TEAEs leading to dose modification, TEAEs leading to drug withdrawn, TEAEs leading to death will be summarized in a similar manner.

Summaries tables will be sorted by decreasing frequency of subjects within each SOC and then similarly by decreasing frequency of subjects within each PT. In the case of equal frequency of number of subjects in SOCs or PTs, summaries will be sorted in descending order. Sorting will be based on the total frequency in the combination therapy arm for safety [REDACTED] summaries, and across both arms for all other tables, unless stated otherwise.

Myelodysplastic syndrome (MDS) or Acute myelogenous leukemia (AML) are considered AESIs. These are applicable only to participants treated with olaparib will be listed with details if they occur.

If a SOC or PT was reported more than once for a subject, the subject would only be counted once in the incidence for that SOC or PT.

All AEs, SAEs, DLTs, and will be listed by patient, along with information regarding onset, duration, relationship and severity to study drug, action taken with study drug, treatment of event, and outcome.

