Review of dosing diary ^z				X		X		X	X	X		X			
AE assessment			During Screening, only AEs considered related to trial procedures or SAEs need to be reported. Following initiation of dosing AE to be collected through 30 days after the last dose of trial intervention or start of new anticancer therapy, whichever is earlier. SAEs believed to be due to trial treatment should be reported through the end of trial date or whenever the Investigator becomes aware thereafter.												
Concomitant medications/procedures			To be collected from the time of Screening visit through the Safety Follow-up visit												
Transfusion and growth factors			If administered, to be collected from the time of Screening visit through the Safety Follow-up visit												
Post-trial therapy data collection															X
Survival status															X
Secondary hematologic malignancy status															X

AE = adverse event; BID = twice daily; CA-125 = cancer antigen 15, CT = computed tomography; ctDNA = circulating tumor DNA; CXDX = Cycle X Day X, Disc of Trt = Discontinuation of treatment; ECG = electrocardiogram; ECOG = Eastern Cooperative Oncology Group; EOT = end of treatment; ICF = informed consent form; MRI = magnetic resonance imaging; NGS = next-generation sequencing; PCWG3 = Prostate Cancer Working Group 3; PE = physical examination; PK = pharmacokinetic; PSA = prostate-specific antigen; RECIST = Response Evaluation Criteria in Solid Tumors; SAE = serious adverse event;

WOCBP = women of childbearing potential

a. **Screening:** Screening Period extends from Day -30 to Day -3. Screening laboratory assessments (hematology, chemistry, urinalysis, and serum tumor marker) may be used as Day -2 assessments if performed within 48 hours of the first dose of trial intervention. ECOG performance status and PE that are completed within 24 hours of first dose of trial treatment may be used as Day -2 assessments. Procedures that are to be performed as part of the practice of medicine and which would be done whether or not trial

entry was contemplated, such as for diagnosis or treatment of a disease or medical condition, may be performed and the results subsequently used for determining trial eligibility without first obtaining consent. Participants must continue to meet eligibility criteria prior to the first dose of RP-3467 on Day -2.

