- b. **EOT Visit:** An End-of-Treatment visit will be conducted following the last dose of trial intervention and within +7 days of the discontinuation of treatment date. If a participant comes to the clinic to start a new cycle but the decision is made to discontinue treatment, that visit may be used as the EOT visit. The EOT visit should occur prior to the start of subsequent anticancer treatment.
- c. **Safety Follow-up:** Required for all participants who discontinued from treatment for whatever reason. The window for the Safety Follow-up visit will be 30 (+14) days from the last dose of trial intervention.
- d. **Long-Term Follow-Up:** Follow-up will be conducted at approximately 3, 6, 12, 18, and 24 months (\pm 14 days) after the discontinuation of treatment date. This follow-up will be conducted by telephone contact or standard method used by participating centers and agreed by the Sponsor. This does not require an in-person visit. Information regarding post-trial therapy, survival status, and hematologic malignancy diagnosis will be collected. The Long-term follow-up period may end sooner if a participant is diagnosed with a hematologic malignancy or if death is known to have occurred prior to 24 months.
- e. **C1D8 and C1D9:** A +2 day window is allowed for the C1D8 visit. If a window is used for C1D8, the same window should be used for C1D9.
- f. **CXD1:** The start of a new additional cycle should always coincide with the start of trial intervention administration for that cycle. A +3-day window is allowed for the start of new cycles, though cycles should never start early and should be at least 21 days in length. A -2 day window is allowed for the safety assessments scheduled for the CXD1 visit to enable flexibility with visit scheduling.
- g. **CXD8:** Hematology and vital signs to be assessed only on Cycles 2 and 3.
- h. **Molecular Eligibility:** NGS reports will be emailed to the Sponsor-approved central annotation group for central review to confirm molecular eligibility.
- i. **Abbreviated PE:** Starting at Cycle 2, abbreviated PE to be performed every 2 cycles (unless full PE necessary by Investigator judgment).
- j. **Vital Signs:** Blood pressure, heart rate, and temperature to be measured after the participant has been sitting for 5 minutes.

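### SAP 10.2 limits the MDS/AML listing to olaparib-treated participants, so a late case after RP-3467 alone that is not reported as a treatment-related SAE has no planned output in the available SAP text

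*SAP*

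**What the plan says.** SAP Section 10.2 (Adverse Events) states: "Myelodysplastic syndrome (MDS) or Acute myelogenous leukemia (AML) are considered AESIs". The next sentence sets the scope: "These are applicable only to participants treated with olaparib will be listed with details if they occur". It is grammatically broken, but both the AESI status and the detailed listing are tied to olaparib treatment. The overall AE summary in the same section has a row for "Adverse Event of Special interest (AESI) if any occurred as defined in the protocol".

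Collection is wider than that. SAP Section 12, Table 5, which covers Arms 1 and 2, has a long-term follow-up row headed "Secondary hematologic malignancy status". Its footnote d says "Follow-up will be conducted at approximately 3, 6, 12, 18, and 24 months" after treatment is discontinued, and "Information regarding post-trial therapy, survival status, and hematologic malignancy diagnosis will be collected". Neither the row nor the footnote is restricted by arm. The Arm 2 schedule (Table 6) carries the same row and footnote.

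Ordinary AE collection is shorter. Under SAP Section 10.2 it runs "until 30 days after last trial intervention administration or until participant started alternative anticancer therapy, whichever is sooner". After that point, the AE row of Table 5 asks sites to report only SAEs they attribute to trial treatment. Section 10.2 counts RP-3467-related SAEs as TEAEs whenever they begin.

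**The concern.** The trial follows every participant for secondary hematologic malignancy, but the one analysis rule dedicated to MDS/AML covers only those who took olaparib. The primary objective (Protocol Section 1.1, SAP Section 3.1.1) is the safety of RP-3467 alone as well as in combination, and Arm 1 is the only group treated without concurrent olaparib. Protocol exclusion criterion 11 excludes previous or current MDS/AML, or suggestive features, in both arms, so the condition already matters trial-wide.

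Two things are at stake. First, the AESI row and listing cannot be compared between monotherapy and combination, because one side is empty by rule. Second, whether a late monotherapy case is reported at all depends on an individual causality judgment. Attribution to earlier treatment is a realistic alternative: participants generally enter after prior systemic therapy, and the SAP's prior-therapy summary has entries for prior platinum and prior PARP inhibitor. Long-term follow-up exists to find late cases, and those are the ones most exposed to this gap.

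**Working it through.** The plan gives no figure on this point and none is needed. The check traces an MDS/AML case in a participant who has received only RP-3467 through the SAP's own rules.

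**Rules used**
- Safety Population (SAP 4.2): anyone given at least one dose of RP-3467, so monotherapy is included.
- AE window (SAP 10.2): "AEs will be collected and recorded for each patient from the day of signing the ICF until 30 days after last trial intervention administration"; the window closes earlier if other anticancer therapy starts first.
- Late events (SAP 10.2 and the AE row of Table 5): only SAEs attributed to trial treatment are still reported; those related to RP-3467 are TEAEs at any onset.
- Causality (SAP 10.2): if missing and not resolved by query, it is taken as related.
- General outputs (SAP 10.2): TEAEs are tabulated by SOC and PT, and all AEs and SAEs are listed by patient.
- AESI outputs (SAP 10.2): olaparib-treated participants only.
- Long-term follow-up (Table 5, footnote d): malignancy diagnosis in all participants, to 24 months.

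**Routes**
1. *Onset on treatment or within 30 days of the last dose, before new anticancer therapy.* The case is in the TEAE tables and the AE listing. It is absent only from the AESI row and AESI listing.
2. *Later onset, reported as an SAE, judged RP-3467-related or with causality unresolved.* The case counts as a TEAE and is listed. Again it is absent only from the AESI outputs.
3. *Onset more than 30 days after the last dose, or after new anticancer therapy, and not reported as a treatment-related SAE* (judged unrelated, or not reported as serious). The case is outside AE collection, is not a TEAE and is not an AESI. It is recorded only as malignancy status in long-term follow-up.
4. *Crossover to the combination before the event.* The participant is now olaparib-treated, so the AESI rule applies.

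**Is there an output for route 3?** The SAP contents list gives safety Sections 10.1 to 10.6: DLTs, adverse events, laboratory tests, vital signs, ECG and performance status. All six are present in the text. None plans a table or listing of the long-term malignancy data. Sections 7 to 9 are not in the available copy, so the statement is limited to what can be read.

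**Size of the group.** SAP Section 2.3 plans about 12 participants for monotherapy escalation. The number who never receive olaparib is about 12 minus those who cross over after progression. The documents give no expected crossover number and no expected MDS/AML rate, so the chance of a route 3 case cannot be calculated.

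**The case against.** The strongest reply is that AESI status is not the only way into the report. The TEAE tables, the all-AE/SAE listing, the any-onset rule for RP-3467-related SAEs and the missing-causality rule all apply to monotherapy participants. That stands, and it removes routes 1 and 2 from any claim of omission. A reader might infer that a case after RP-3467 alone would be missing from every table and listing. The documents do not support that; only route 3 drops out.

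A second reply is that the argument rests on absence. SAP Sections 7 to 9 and the protocol's AESI section are not in the available text, and follow-up data might be reported there. This stands as a limit on certainty. It does not touch the restriction in Section 10.2, which is written out.

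A reader might also infer that the SAP assumes only olaparib can cause MDS/AML, or that the data are lost. Neither follows. Section 10.2 limits a reporting category and says nothing about cause, and the follow-up data are still to be collected; what is missing is a specified output. Nor is Arm 1 assured to be free of earlier PARP-inhibitor exposure, so a single late case would be hard to attribute under any rule. That is a reason to read a listing cautiously, not a reason to omit the case.

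Finally, AESI scope is partly the sponsor's choice and is taken from the protocol. That is fair. Complete reporting needs a listing, not necessarily a wider AESI definition.

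**Conclusion.** The point holds in a limited form. Section 10.2 confines the MDS/AML AESI and its listing to olaparib-treated participants, while the schedule collects hematologic malignancy in everyone for up to 24 months after discontinuation. Every monotherapy case is therefore absent from the AESI row and listing. A late one not reported as a treatment-related SAE also has no output in the visible SAP.

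The affected group is small: the part of an arm of about 12 that never takes olaparib. The number of cases may well be zero, and no rate should be inferred. The conclusion assumes that the missing SAP sections add no listing of these data and that the protocol's AESI definition matches the restriction in SAP 10.2. It is a low-cost improvement to safety reporting and not a flaw in the design.

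**What to change.** In SAP Section 10.2, replace the olaparib-only listing with a listing of every MDS/AML or other secondary hematologic malignancy in the Safety Population, from first dose to end of trial. Include cases regardless of causality and those found in long-term follow-up. Group them by treatment received (RP-3467 alone, combination, crossed over), and give time from first dose and from last dose. Rewriting the sentence also repairs its grammar and settles whether follow-up data feed the listing for olaparib-treated participants, which the current text leaves open.

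Keep the formal AESI definition consistent with the protocol. If the protocol limits it to olaparib, the listing can stand beside the AESI row without changing it.

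The cost is one sentence and one additional listing from data already scheduled for collection, with no change to visits or clinical management. The small downside is that the listing will include cases that investigators attribute to earlier therapy, so it should show the reported causality and be read as description only.

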10.3 Clinical Laboratory Tests

Hematology and serum chemistry parameters will be summarized for Safety population.

For all quantitative parameters, the actual value and the change from baseline will be summarized by dose level and dose schedule (if applicable) for each study visit using descriptive statistics. Both scheduled and unscheduled visits will be considered for baseline derivation.

Laboratory parameters are also graded according to CTCAE v5.0. A shift table, presenting the 2-way frequency tabulation for baseline and the worst post-treatment value (during the treatment emergent period) according to the NCI-CTCAE grade will be provided for these selected parameters outlined in Table 4. Both scheduled and unscheduled post-treatment visits during the treatment period and up to 30 days past the last dose date will be considered in tabulation of the worst post-treatment value. Additionally, the number and percentage of participants with the following potentially clinically significant abnormal liver function test will be presented. Corresponding listing for patients meeting below criteria:

- ALT $>3\times$ ULN, $\geq 5\times$ ULN, $\geq 10\times$ ULN, and $\geq 20\times$ ULN
- AST $>3\times$ ULN, $\geq 5\times$ ULN, $\geq 10\times$ ULN, and $\geq 20\times$ ULN
- Total bilirubin $\geq 2\times$ ULN

Table 4 Laboratory Tests Included in Summary Shift Tables

Category	Parameter	CTCAE Terms
Chemistry	Alanine Aminotransferase	Alanine Aminotransferase increased
	Albumin	Hypoalbuminemia
	Alkaline phosphatase	Alkaline phosphatase increased
	Aspartate Aminotransferase	Aspartate Aminotransferase increased
	Bilirubin	Blood bilirubin increased
	Creatinine	Creatinine increased
Hematology	Hemoglobin	Anemia
	Leukocytes	White blood cell decreased
	Neutrophils	Neutrophil count decreased
	Platelets	Platelet count decreased

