5.2 Definition of Treatment Emergent Period

Unless otherwise stated, derivations of the worst post-treatment value will be assessed within the confines of the treatment emergent period, defined as the time from the start of study treatment, until 30 days after the last dose of RP-3467 or olaparib, the participant starts a subsequent anti-cancer therapy, or the participant is taking the monotherapy treatment and starts olaparib treatment, whichever occurs first.

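### SAP 10.3 gives two non-identical windows for the worst post-treatment laboratory value, and the second omits the cuts at olaparib start and at subsequent therapy

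*SAP*

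**What the plan says.** SAP 5.2 sets the general rule: "derivations of the worst post-treatment value will be assessed within the confines of the treatment emergent period". It opens with a proviso that it yields where the plan states something else. The period closes 30 days after last dose or when new anticancer therapy begins, and 5.2 adds a third limit: "or the participant is taking the monotherapy treatment and starts olaparib treatment, whichever occurs first".

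SAP 10.3 builds the shift table from the baseline grade and "the worst post-treatment value (during the treatment emergent period) according to the NCI-CTCAE grade". The sentence immediately after it, on the same statistic, reads "Both scheduled and unscheduled post-treatment visits during the treatment period and up to 30 days past the last dose date will be considered".

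The counts of participants crossing ALT, AST and bilirubin thresholds, introduced next in 10.3, have no window of their own.

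**The concern.** Two consecutive sentences define the same quantity with different end dates. The second repeats one of the three limits in 5.2 and is silent on the other two. Because 5.2 gives way to contrary statements, a programmer could reasonably treat the second sentence of 10.3 as one.

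The limit on olaparib start matters most. The protocol synopsis lets Arm 1 participants move to RP-3467 plus olaparib after progression, and it acknowledges that olaparib has toxicity of its own that can confound the picture. If values from that stage are admitted, a low blood count or raised transaminase on the combination can be shown as the worst grade for an RP-3467 monotherapy dose level. The TEAE table would generally leave out the matching event, so two safety outputs for the same person could disagree.

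**Working it through.** The plan states no figure to reproduce. The check compares the texts, then counts days on assumed dates, then sizes the effect.

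**1. The limits side by side**

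| Limit on the worst value | Period in SAP 5.2 (first sentence of 10.3) | Second sentence of 10.3 |
|---|---|---|
| 30 days after last dose | Yes | Yes |
| Start of subsequent anticancer therapy | Yes | Not stated |
| Olaparib start in a monotherapy participant | Yes | Not stated |

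**2. Does the term treatment period itself exclude the rescue stage?** It does not appear to. SAP 2.2 describes the Treatment Period only as 21-day cycles. SAP 6.6.6 summarises relative dose intensity over the whole treatment period and then adds an explicit cut at the start of rescue. That cut would be unnecessary if the term already excluded rescue. Nor does it help to read last dose as the last RP-3467 dose, because a crossover participant continues RP-3467 alongside olaparib.

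**3. What related sections do**
- SAP 10.2 ends the TEAE window at olaparib start in a monotherapy participant. RP-3467-related SAEs are excepted and count whenever they begin.
- SAP 10.5 limits the ECG shift tables to the treatment-emergent period and adds no second window.
- SAP 6.6.6 cuts relative dose intensity at the start of rescue.

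Among these, only the laboratory section carries a competing sentence.

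**4. Difference in days (assumed dates, for illustration only)**
- Crossover: olaparib starts Day 85 and the last dose is Day 168. The 5.2 period ends Day 85. The second window ends Day 168 + 30 = Day 198. Excess: 198 − 85 = 113 days, all after olaparib has begun.
- Early new therapy: last dose Day 168, new therapy Day 182. The 5.2 period ends Day 182 and the second window Day 198. Excess: 198 − 182 = 16 days.
- Neither event: excess 0 days.

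In general the excess is 0 to 30 days for early new therapy. For crossover it is the whole rescue stage plus up to 30 days.

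**5. Size in the table.** Widening the window can only leave a worst grade unchanged or raise it. Inputs: up to 3 participants initially per Arm 1 level (protocol synopsis); up to 9 DLT-evaluable participants at a level (SAP Table 2); about 12 planned in Arm 1 (SAP 2.3). One participant whose worst grade changes moves a cell by:
- 1/3 = 33 points at a level of 3
- 1/9 = 11 points at a level of 9
- 1/12 = 8.3 points for Arm 1 overall

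**6. How wide is the subsequent-therapy route?** Under the schedule of activities, the end-of-treatment visit should come before new therapy, and Safety Follow-up falls on Day 30 to Day 44 after last dose. Values from Day 31 to Day 44 lie outside both windows. That leaves mainly unscheduled tests up to Day 30. SAP 2.2 instead gives 30 ± 14 days for this visit, so it could fall as early as 30 − 14 = Day 16. If that applies, the route is wider.

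**The case against.** The strongest reply is that the two sentences nest. The first fixes the period. The second only says which visit types feed a value already defined, in parallel with the statement in 10.3 that scheduled and unscheduled visits both count for baseline, and with SAP 5.5 on unscheduled data in laboratory grading. To reach the harmful result, a programmer must set aside an explicit parenthesis one sentence earlier. This reading is probably the intended one. It does not remove the problem, because the second sentence states an end date of its own and that date differs from the one in 5.2.

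The reply is also right to limit the consequences. A reader might infer any of the following, and the documents support none of them:
- **That monotherapy toxicity will be overstated.** This follows only if the second sentence is programmed literally.
- **That about 12 participants are exposed.** Twelve is the planned Arm 1 total and so only a ceiling. Crossover also requires progression, eligibility, no drug-related toxicity above Grade 2 on monotherapy, and Medical Monitor approval.
- **That dose finding is affected.** DLTs are confined to Cycle 1, and the primary endpoints are DLTs and TEAEs.
- **That the TEAE tables exclude every post-crossover event.** The exception for RP-3467-related SAEs means they do not.
- **That rescue-stage laboratory results are never summarised.** SAP 5.3 defines a rescue period, and the public SAP is redacted, so such a summary may exist.

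For the liver-test counts, 5.2 can reasonably be taken as the default, since crossing a threshold is in effect a worst-value derivation. Stating that would settle it.

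**Conclusion.** The inconsistency is real, and minor. SAP 10.3 gives two windows that differ for Arm 1 crossover participants and, more narrowly, for anyone in either arm who starts new therapy within 30 days of last dose. The crossover route is the one that justifies an edit, because it can attribute values obtained on olaparib to a monotherapy dose level.

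The per-participant sizes above rest on three assumptions: the second sentence is programmed as written; the crossover participant is tabulated under the original Arm 1 level; and the worst grade occurs after olaparib start. The 33-point figure is the extreme case of a three-person level. No total effect can be given without a crossover rate. The tables are descriptive and no escalation rule uses them.

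**What to change.** Reword the second sentence of SAP 10.3 along these lines: *Both scheduled and unscheduled visits within the treatment-emergent period defined in Section 5.2 will be considered.* State that the same window applies to the ALT, AST and bilirubin threshold counts.

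The cost is one or two sentences of SAP text, plus a date filter using the cuts already needed for TEAEs. It is best done before the tables are programmed. A separate shift table for the rescue period is optional, and unnecessary if the redacted text already provides one.
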